2.2.3 Rationale for the Evaluation of GEN1053 in Combination With an IM

To improve the antitumor efficacy of CCI, n	nost of the current CC
in clinical development are evaluating combination strateg	
anticancer therapies, including T-cell costimulatory receptor agonists	
Activation of T-cell costimulatory receptors (ie, CD27 CCI)) can amp	lify the effect of
, as shown nonclinically and in CC	
	therapy may develop
CCI	
Costimulation through CC	may support
re-establishing antitumor immunity in this patient population CC	

Confidential

CCI . CD27 costimulation in combination with CCI showed clinical activity in tumor types resistant to CCI . In addition, CD27 in combination with CCI leading to tumor growth inhibition that was not seen with either CD27 CCI monotherapy. CCI	
T-cell costimulation via CCI agonistic antibodies alone can enhance antitumor memory T-cell survival resulting in longer lasting protective immunity against the tumor CCI antibodies can complement T-cell costimulation CCI , which may improve antitumor responses in patients with insufficient baseline T-cell activation CCI . Therefore, it is hypothesized that coactivation of CD27 with CCI may further improve antitumor responses and thereby the clinical benefit for patients.	
CCI	
• CCI	
• CCI	
• CCI	

Additional details including results from nonclinical combination studies, are provided in the GEN1053 IB and any updates thereof.

The optimal combination partner(s) will be selected based on the monotherapy safety profile of GEN1053 and emerging data from the compounds **CCI**. The protocol will be amended before initiating the combination therapy Dose Escalation phase 1b.

2.2.3.1 Summary of Nonclinical Studies – Combination Therapy

A nonclinical data package, consisting of nonclinical pharmacology studies in vitro and ex vivo is available for the combination of GEN1053 with CC

Nonclinically, GEN1053 in combination with CCl showed increased capacity to increase proliferation and cytokine production in activated T cells in vitro. In addition, combination of GEN1053 with CCl enhanced cytotoxicity in vitro and

expansion of TIL, particularly CD8⁺ T cells, from NSCLC tumor tissue ex vivo (GEN1053 IB, Section 3).

2.2.4 Summary of Clinical Trials to Date and Experience With CD27-Targeting Agents

2.2.4.1 GEN1053 Clinical Trials

This is the FIH trial of GEN1053. There are no other ongoing or completed clinical trials.

2.2.4.2 Experience With CD27-Targeting Drugs

To date, other CD27-targeting mAbs in clinical development, varlilumab (CDX-1127, Celldex Therapeutics) and MK-5890 (Merck), have shown early antitumor activity in subjects with advanced solid tumors in monotherapy **CC**

. Importantly, they have demonstrated an acceptable safety profile in FIH trials as monotherapy CCI.

In clinical safety data from other CD27-agonist compounds studied in monotherapy for solid tumors, the most frequently observed AEs included fatigue, rash, nausea, diarrhea, pruritus, and IRRs. Most of these events were mild or moderate in severity. Refer to the GEN1053 IB for available safety information from other CD27-targeting agents.

2.3 Benefit-Risk Assessment

2.3.1 Potential Benefit

2.3.1.1 Potential Benefit of GEN1053

Based on nonclinical data and published clinical data regarding other agents that target human CD27 mAbs in various tumor types, clinical antitumor activity can be expected for GEN1053. Therefore, cancer patients with limited treatment options, and for whom the investigator agrees that clinical trial participation is appropriate, may benefit from treatment with GEN1053.

2.3.1.2 Potential Benefit of GEN1053 in Combination With IM

Based on their respective MoAs, it is hypothesized that the combination of GEN1053 with an IM will enhance the antitumor activity as compared with GEN1053 monotherapy (Section 2.2.3.1).

Further details will be provided in a substantial amendment before initiating phase 1b of the trial.

2.3.2 Potential Risks

2.3.2.1 Potential Risks of GEN1053

The nonclinical studies performed with GEN1053 demonstrated thrombocytopenia, bleeding, anemia, and increased plasma levels of ALT, AST, and LDH with delayed onset in monkeys. The exact MoA has not yet been determined. However, there was no cytokine release, hemocompatibility issues, or direct binding of GEN1053 to human or cynomolgus monkey platelets and erythrocytes detected. Possible mechanisms could be platelet aggregation caused by

GEN1053-induced ADAs that were rapidly cleared due to immune complex formation and thus not detected, or CD27-related exaggerated pharmacology affecting the lymphoid cells and bone marrow function at the high dose levels employed in the monkey studies. Overall, based on the observed toxicities in monkeys, additional safety measures will be taken when exploring GEN1053 in the first clinical trial.

A mitigation plan for handling AEs, including elevated liver parameters, CRS, IRRs, and thrombocytopenia, related to the trial treatment has been prepared for this trial to closely monitor for and ensure dose delay, dose reduction, or withdrawal of subjects based on AEs that may occur during trial treatment (Section 6.7.2).

Risk mitigation strategies are provided in Section 6.7.2 and summarized in Section 2.3.3.

Targeting CD27 has not in itself led to unacceptable toxicities or safety concerns with other compounds in clinical development (see Section 2.2.4.2).

Potential subjects will be fully informed of the risks and requirements of the trial, and during the trial, subjects will be given any new information that may affect their decision to continue participation. They will be told that their consent to participate in the trial is voluntary and may be withdrawn at any time with no reason given and without penalty or loss of benefits to which they would otherwise be entitled. Only subjects who are fully able to understand the risks, benefits, and potential AEs of the trial and provide their consent voluntarily will be enrolled.

GCT1053-01 phase 1a data showed an increased frequency of severe cytopenias and severe transaminase increases in subjects treated with GEN1053 with prior anti-PD-1/PD-L1 exposure within the last 6 months. Due to this potential risk subjects treated with anti-PD-1/PD-L1 within the last 6 months are excluded from participation in the trial.

Further details are provided in the IB and its updates thereof. Currently, there are no anticipated events for GEN1053 described in the reference safety information. Additional safety information collected between IB updates will be communicated in the form of investigator notifications.

2.3.2.2 Potential Risks of Immunomodulators

For combination therapy, the potential risk of overlapping toxicities depends on the MoA of the therapies to be combined with GEN1053. When the IM has been selected, such risk consideration will be made, and a substantial amendment of this protocol will be submitted and subject to approvals by health authorities and IRBs/ethics committee prior to initiating the GEN1053+IM combination Dose Escalation phase 1b of the trial.

2.3.3 Conclusion

Based on the interpretation of the nonclinical data available to date, published data from other CD27-targeting agents, and the potential IM candidates, the conduct of this trial investigating GEN1053 monotherapy and GEN1053+IM sequentially is regarded as justifiable.

A cautious approach will be applied for dose escalation from CCI in this FIH trial with strict DLT criteria, adequate AE management, and safety stopping rules in place (see Sections 6.7.1 and 6.7.2).

The population eligible for the current trial represents subjects with selected malignant solid tumors, who have failed available standard therapy or who are not candidates for standard therapy, and for who, in the opinion of the investigator, experimental therapy with GEN1053 or GEN1053+IM may be beneficial. The trial population is defined to include only subjects with a platelet count $\geq 150 \times 10^9/L$ at baseline. Subjects with known platelet function defects or a known history or high risk of bleeding events requiring transfusions or hospitalizations will also be excluded from the trial.

Events to be closely monitored for GEN1053 include thrombocytopenia, bleeding episodes, elevated liver parameters, irAEs, and IRRs. The DEC (during the escalation phases 1a and 1b) and the SC (throughout the trial) will closely monitor subject safety as described in Appendix 1. In addition, an independent DMC will further supervise that the safety of the subjects in this trial is properly safeguarded, acting as an external advisory body (Appendix 1).

Subjects enrolled will have frequent visits and will be monitored closely by site staff and via medical monitoring throughout the trial. An elaborate risk mitigation plan for handling potential AEs has been prepared (and will be updated for phase 1b as deemed necessary) in order to manage AEs, delay the dose, or discontinue treatment based on AEs that may occur with GEN1053 and the selected IM(s) (Section 6, Table 6-2, Table 6-3 and Table 6-4). The anticipated combined safety profile will be carefully assessed prior to the start of the combination therapy Dose Escalation phase 1b with focus on potentially overlapping toxicities.

All subjects enrolled in this trial will be followed and monitored by qualified health care professional(s) who will provide care and closely evaluate each subject's response to GEN1053 and GEN1053+IM both in terms of safety profile and efficacy.

Collectively, the benefit-risk ratio is considered favorable for GEN1053.

The sponsor is committing to sharing relevant monotherapy safety data from the monotherapy Dose Escalation phase 1a part with the health authorities and to submitting a substantial amendment before initiating the phase 1b combination Dose Escalation part of the trial.

For further details on GEN1053, refer to the IB.

Objectives and endpoints by study part are summarized in Table 3-1.

Table 3-1 Objectives and Endpoints

OBJECTIVES	ENDPOINTS			
Primary				
 Determine MTD/MAD/RP2Ds of GEN1053 as monotherapy and in combination with IM Establish initial safety profile of GEN1053 as monotherapy and in combination with IM 	 DLT(s) (Dose Escalation parts only) AEs and safety laboratory parameters 			
Secondary				
Establish PK profile of GEN1053 as monotherapy and in combination with IM	• PK parameters for GEN1053: CL, V, C _{max} , t _{max} , C _{trough} , t _{1/2} , AUC _{last} and AUC _{tau}			
Evaluate immunogenicity of GEN1053 as monotherapy and in combination with IM	 Antidrug antibody response to GEN1053 and in combination with IM 			
 Evaluate antitumor activity of GEN1053 as monotherapy and in combination with IM 	 Antitumor activity according to RECIST 1.1: ORR DCR DoR 			
Exploratory				
• To assess pharmacodynamics, potential response and safety biomarkers for GEN1053 as monotherapy and in combination with IM	 Immune system activation (eg, immune subset shift, modulation of activation markers on lymphocytes, changes in TCR clonality, and tumor immune cell infiltration) 			
• To assess antitumor activity based on iRECIST of GEN1053 as monotherapy and in combination with IM	 Antitumor activity according to iRECIST iORR iDCR iDoR iPFS 			
Evaluate efficacy of GEN1053 as monotherapy and in combination with IM	 PFS OS 			
 To assess tumor growth with GEN1053 as monotherapy and in combination with IM 	Change in tumor size			

Hypotheses:

The Dose Escalation parts of the trial aim to describe the relationship between dose and toxicities without testing hypotheses. The Expansion part will generate hypotheses regarding efficacy, ORR, and regarding PFS, DCR, and DoR.

Details on statistical considerations are provided in Section 9.

4 TRIAL DESIGN

4.1 Description of Trial Design

This is a FIH phase 1/2a open-label, multicenter, multinational trial in subjects with non-CNS metastatic or advanced solid tumors for whom there is no available standard therapy likely to confer clinical benefit, evaluating the safety, tolerability, preliminary antitumor activity, PK, pharmacodynamics, and immunogenicity of GEN1053 as monotherapy as well as in combination with IM.

The trial will be conducted with a Dose Escalation part (phase 1a and 1b) and an Expansion part (phase 2a) as follows:

- Phase 1a Monotherapy Dose Escalation
- Phase 1b Combination therapy Dose Escalation
- Phase 2a Expansion

The Dose Escalation part will explore the safety of escalating doses of GEN1053 as monotherapy (phase 1a) as well as escalating doses of GEN1053 when combined with a fixed dose of an IM (phase 1b) in a sequential approach in a population of subjects with various solid tumors.

The sponsor will share relevant monotherapy safety data from phase 1a with the health authorities and submit a substantial amendment before initiating the combination Dose Escalation phase 1b.

The Expansion part is planned to provide additional safety and initial antitumor activity information of the RP2Ds for GEN1053 monotherapy and GEN1053+IM combination therapy, respectively, in selected tumor indications. In the first Expansion cohort (HNSCC), more detailed data related to the MoA of GEN1053 monotherapy will be generated. Upon PD while on GEN1053, and provided that the RP2D for the combination has been determined in phase 1b, subjects will have the option to cross over to GEN1053+IM to explore the effect of sequencing the trial treatments. In the second Expansion cohort, GEN1053+IM will be evaluated in subjects with NSCLC.

Each part will consist of a screening period (up to 21 days prior to C1D1), a treatment period (C1D1 until discontinuation of trial treatment), and 2 safety follow-up visits 30 days and 60 days after each subject receives the last dose of trial treatment, preceding the survival follow-up. Subjects will be treated in cohorts, defined as a group of subjects allocated to the same treatment.

Both GEN1053 and IM will per default be administered as an IV infusion in 3-week (ie, 21-day) cycles (Q3W) (refer to Section 6, Trial Treatment) until PD, unacceptable AE, or withdrawal of consent (refer to Section 7.1).

The protocol may be amended to explore additional doses/schedules and combination compounds both during Dose Escalation and/or in separate Expansion cohorts based on emerging data. Randomization between relevant doses/schedules will be considered in the

Expansion part. Such an amended protocol will be submitted as a substantial amendment prior to initiation.

The safety, tolerability, immunogenicity, PK, pharmacodynamics, and biomarkers will be assessed together with the clinical activity of GEN1053 or GEN1053+IM. Assessments, biomarkers, PK, and ADAs will be evaluated as detailed in the Schedule of Activities, Section 1.3.

A trial-independent DMC, an SC, and a DEC will be commissioned for this trial. Refer to the Committees Structure section of Appendix 1 for details.

During the Dose Escalation part, DLTs will be assessed by the DEC in the first treatment cycle of each DL. In case a DLT has been observed at the current dose level, the DEC will assess whether escalation by a half or a full DL is appropriate, depending on the nature of the observed DLT, and supported by the BLRM approach, which is used to make dose recommendations and estimate the MTD during the Dose Escalation part of the trial. The DEC will also assess all available data with focus on safety events that meet DLT criteria but occur after the DLT period in any subject according to the DEC Charter and make recommendations for the next DL and/or propose the RP2D/MTD/MAD to the DMC and the SC. The DMC will assess the totality of information of the trial to propose whether the trial can proceed to the subsequent design phase according to the DMC charter. The SC will make the final decision regarding dose escalation (or de-escalation) and/or the continuation of the trial to its next design phase.

During the Expansion phase of the trial, the SC will make decisions regarding the progression of the trial based on benefit-risk considerations. The SC can also stop further enrollment if treatment-emergent toxicity is determined to result in an unfavorable benefit-risk assessment for subjects. Enrollment may be temporarily stopped, if needed, for the SC to evaluate emerging data. In case of emerging safety issues with potential impact on the trial conduct, the SC will inform and consult the DMC on an ad hoc basis.

The decision process will be guided by the principles outlined in Section 4.2.1 and 4.2.2.

A diagram of the trial design is provided in Section 1.2.

Patient input into trial design was not obtained for this trial.

4.2 Trial Design Rationale

4.2.1 Dose Escalation (GEN1053 Monotherapy)

In the Monotherapy Dose Escalation phase 1a, GEN1053 will be evaluated in non-CNS metastatic or advanced malignant solid tumors. At each DL, DLTs will be assessed in the first treatment cycle, ie, a DLT evaluation period of 21 days from C1D1.

The Monotherapy Dose Escalation will potentially (dependent on data collected during the trial) evaluate CC

. GEN1053 will be dosed Q3W.

There will be a minimum of 2 nights between the first and second subject at each DL to account for any acute safety signals. An overnight stay will be required for the first subject at each DL

and may be required for additional subjects. Furthermore, no subjects within a cohort will receive their first treatment simultaneously, ie, on the same day during dose escalation except for DLs declared safe by the SC which are further investigated by backfilling.

Identification of MTD/MAD (Monotherapy):

To address the trial objectives in this FIH trial, the Monotherapy Dose Escalation phase 1a will be initiated in single-subject cohorts for the first 2 DLs followed by 3-subject cohorts for subsequent DLs. However, a 1-subject cohort will be converted to a 3-subject cohort if any of the following events are observed:

- Any grade ≥2 AE within the first 21 days of Cycle 1, unless clearly related to underlying disease or extraneous causes.
- A DLT (see Section 6.7.1) within the first 21 days of Cycle 1.

If cohort conversion occurs at the first DL, the subsequent DLs will be explored in 3-subject cohorts with the option to expand as described below.

To aid in determining the DL for the next cohort, the relationship between the probability of DLT and DL will be described by a 2-parameter BLRM with overdose control (EWOC) (Babb et al., 1998; Neuenschwander et al., 2008). After each cohort, the model parameters will be updated based on the available DLT information and a DL for the next cohort suggested based on the posterior distributions of probabilities of DLTs at each DL. Compared to the standard 3+3 and accelerated titration designs, the BLRM provides both more flexibility and better accuracy of the estimated MTD while ensuring subject safety.

All escalations are constrained (ie, a new DL can only be 1 step higher than the previous DL [intermediate DLs will count as half a step]). De-escalations can skip DLs. The dose escalation is limited to only main DLs until the first DLT is observed; thereafter the intermediate DLs become available. Backfilling of intermediate DLs may also be considered.

The following provides a description for subject accrual and provisions for dose escalation/deescalation decision guidance.

- 1. After completion of Cycle 1 of each cohort, based on the cumulative safety data and the BLRM, the SC will endorse the DL for the next cohort of subjects.
- 2. The initial 2 DLs will be single-subject cohorts. In case of a treatment-related Grade \geq 2 AE during the first cycle or a DLT (Section 6.7.1), the cohort(s) will be expanded to 3 subjects and the BLRM method will be applied after first DLT.
- 3. A subject will be considered as evaluable for dose determination if they fulfil the criteria of the DDS (refer to Section 9.3.4).
- 4. Once the first DL has been cleared, the BLRM method will be used to support recommendations for the DL for the next cohort, with the following 3 exceptions:
 - o If no DLTs have been observed, escalation may be considered.
 - For cohorts requiring ≥3 evaluable subjects, if only 2 evaluable subjects are available for assessment (all others drop out) and neither subject has experienced a DLT, 2 subjects will

be considered sufficient for decision making.

- If 2 subjects in a cohort experience DLTs, the BLRM model will be updated and reevaluated before the enrollment of any additional subject.
- If a decision has been made to escalate to a higher DL, but 1 or more additional subject(s) treated at preceding DLs (see provision 6) experience(s) a DLT in Cycle 1, then the BLRM will be updated before any additional subject is enrolled to the current (higher) DL.
- 5. Following the principle of EWOC, the BLRM model only allows escalation to DLs that are likely to be safe.
- 6. For further understanding of the safety, tolerability, and PK of GEN1053, additional cohorts of up to 9 subjects may be enrolled at preceding DLs, or at intermediate DLs before or while proceeding with further dose escalation or even thereafter (backfill subjects). Backfill subjects within a DL can receive their first treatment simultaneously.
- 7. A cohort may be expanded to enroll additional subjects. This is in order to ensure availability of sufficient data due to the potential for subjects to discontinue therapy during Cycle 1 without DLT (eg, because of early PD) and allow flexibility.
- 8. After repeating the above steps, the MTD is declared when at least 9 subjects have been evaluated at a DL and the BLRM recommends allocating an additional cohort to the same DL. This DL is the MTD identified by the BLRM. MTD may be declared based on at least 6 subjects if the recommendation is to escalate and the next DL is not available.
- 9. The dose escalation stops when either the MTD has been declared or no doses are considered safe.

More details on the BLRM can be found in Appendix 8.

The SC (after consultation with the DEC and DMC) will determine the MTD and the RP2D based on the BLRM estimate and the totality of data. The MTD and RP2D may be the same as the algorithm recommends for the next cohort or it may be a lower dose.

If there is evidence that a DL lower than the MTD has adequate efficacy (whether determined by scan data, by pharmacodynamic endpoints, or predicted efficacious dose), the DMC may recommend, and the SC may decide, that an RP2D has been determined and may decide to stop the dose escalation.

The overall decision process for the next DL and/or to propose the RP2D/MTD/MAD based on the above guidance is summarized in Section 4.1.

4.2.2 Dose Escalation (GEN1053+IM)

Identification of first GEN1053 dose to be combined with IM: After the MTD/MAD of GEN1053 as monotherapy has been determined, the first GEN1053 DL to be combined with an IM (at a fixed dose) is targeted to be the MTD/MAD minus at least 2 DLs (MTD-2). The selection of the starting DL for GEN1053 for combination with IM will follow the decision process summarized in Section 4.1.

Upon selection of the GEN1053 start dose and IM for combination therapy, a substantial amendment will be issued. This amendment will be subject to approvals by health authorities and IRBs/ethics committees, before initiating phase 1b and the Expansion cohort 2 of this trial.

Dose Escalation Principles for GEN1053+IM

In Combination therapy Dose Escalation (GEN1053+IM) phase 1b, escalating doses of GEN1053 (starting from MTD-2) will be evaluated in subjects with non-CNS metastatic or advanced malignant solid tumors in combination with a fixed dose of an IM using a mBOIN design (Liu and Yuan, 2015). DLTs will be assessed at each DL in the first treatment cycle, ie, a DLT evaluation period of 21 days from C1D1.

The minimum number of subjects treated at each DL is 3. Apart from that, the precautions for subject enrollment within a DL in phase 1a of the trial (Section 4.2.1) also apply for phase 1b of the trial.

A limited number of subjects will be enrolled into phase 1b of the trial. This causes operational challenges on applying a BLRM design, which also tends to be conservative in its choice of MTD. Therefore, escalation and de-escalation in the combination Dose Escalation part will be guided by a mBOIN design. Although similar to the 3+3 design, it adds the ability to 1) investigate a DL multiple times that would have been closed in a 3+3 design; 2) repeatedly escalate and de-escalate; and 3) treat more than 6 subjects at a DL. The mBOIN selects the true MTD at a higher rate and treats a higher percentage of the subjects at the MTD.

The DLT rate for a given DL is estimated as total number of DLTs/total number of subjects treated and qualifying for DDS (at that DL). Based on the accrued data (at each DL), the mBOIN decision guidance rules are supplied in Table 4-1. For further details on the mBOIN methodology, please see Appendix 8.

	Total Number of Subjects Treated at a DL	3	4	5	6	7	8	9
	Escalate	0	0	≤1	≤1	≤1	≤1	≤2
Decision Based on Total Number of DLTs at the DL	Remain	1	1	-	2	2	2	3
	De-escalate	2	2	2	3	3	3	4
	Terminate a DL	3	≥3	≥3	≥4	≥4	≥4	≥5

Table 4-1Modified BOIN Decision Guidance Rules

DL=dose level; DLT=dose-limiting toxicity.

If de-escalation is mandated, GEN1053 will be decreased to the preceding lower main DL while the IM DL per default will be kept fixed during the combination escalation part of the trial. A dose modification of the IM may be proposed by the DEC, the SC, or the DMC in case of emerging safety concerns for the combination treatment. The SC must endorse any such proposal before implementation. A dose modification of IM will be considered a new escalation combination cohort with a similar number of subjects as in other Combination therapy Dose Escalation cohorts. The SC (after consultation with the DEC and DMC) will determine the MTD and the RP2D based on the mBOIN estimate and the totality of data. The MTD and RP2D may be the same as the algorithm recommends for the next cohort or it may be a lower dose.

If there is evidence that a DL lower than the MTD has adequate efficacy (whether determined by scan data, pharmacodynamic endpoints, or predicted efficacious dose), the DMC may recommend, and SC may decide, that the RP2D has been determined and may stop the combination therapy dose escalation.

The overall decision process for the next DL and/or to propose the RP2D/MTD/MAD is summarized in Section 4.1 and will also be based on the above guidance and the principles in Sections 4.2.2.2 to 4.2.2.6.

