4.2.2.2 Dose Level Termination

A potential drawback of the basic BOIN design is that, theoretically, a very toxic DL could be investigated in multiple cohorts if a neighboring DL is not toxic. To avoid this problem, a DL termination criterion will be implemented: A certain DL can no longer be investigated if an additional DLT-free cohort would lead to de-escalation. For example, if there are no DLTs at the current DL, but 3 out of 4 subjects had DLTs at the next higher DL, any outcome would lead to de-escalation (regardless of 0, 1, 2, or 3 DLTs, there would be least 3 DLTs for 7 subjects). All DLs with a higher dose than that of the terminated DL should also be terminated.

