6.7 Dosing Modifications

6.7.1 Dose-Limiting Toxicity

The occurrence of any of the toxicities outlined in this section will be considered a DLT if occurring within the DLT evaluation period, unless clearly related to underlying disease or extraneous causes. The DLT evaluation period is defined as 21 days from the first dose of trial drug, ie, Cycle 1 in the Dose Escalation phase 1a (monotherapy) or phase 1b (combination therapy) of the trial. During the DLT evaluation period, the occurrence of any of the toxicities listed below, which are assessed as related to trial treatment, will be considered DLTs..

Toxicities will be graded for severity according to the NCI-CTCAE, version 5.0. CRS will be evaluated according to the ASTCT criteria (Lee et al., 2019).

General

- All grade 5 events
- Grade 4 anaphylaxis
- Grade 4 IRRs

Hematological events

- Grade 4 neutropenia (ie, ANC $< 0.5 \times 10^9$ cells/L [$< 500/\mu$ L]) for minimal duration of 7 days
- Grade 3 and grade 4 febrile neutropenia (ie, ANC <1.0×10⁹ cells/L with a single temperature of >38.3 °C [100.9 °F] or with a sustained temperature of ≥38 °C [≥100.4 °F] for more than 1 hour)
- Grade 4 thrombocytopenia ($\leq 25.0 \times 10^9$ platelets/L [$\leq 25,000/\mu$ L])
- Grade 3 thrombocytopenia with clinically significant bleeding
- Grade 4 anemia

Non-hematological events:

- Grade 4 AST, ALT, or bilirubin elevation.
- Grade 3 AST, ALT, or bilirubin elevation that does not recover to \leq grade 1 within 14 days.
- AST or ALT elevations ≥ grade 2 with concomitant bilirubin >2.0×ULN with no signs of cholestasis, ie, a Hy's law case.
- Any grade 4 irAE.

- Grade 3 irAEs that do not improve to ≤ grade 1 within 7 days by appropriate care or with corticosteroids except for:
 - Grade 3 pneumonitis, which always qualifies as a DLT.
 - Grade 3 nephritis (defined as inflammation of the kidney affecting the structure associated with grade 3 creatinine increase), which always qualifies as a DLT.
- Grade 4 CRS
- Grade 3 CRS which has not resolved to ≤ grade 2 within 48 hours following adequate intervention (including repeated anticytokine therapy)
- Any other ≥ grade 3 nonhematological AE (including liver toxicities other than increases of transaminases and bilirubin), which occurs during the first GEN1053 treatment cycle *excluding*:
 - Grade 3 fever (>40.0 °C) for \leq 24 hours.
 - Grade 3 hypotension (resolving to baseline or \leq grade 1 within 24 hours).

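### Phase 1b: the stated DLT rate and the Table 4-1 label count DLTs, while the BOIN boundaries and the worked example count subjects with a DLT; the wording should be aligned

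*Combined protocol and SAP*

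**What the plan says.** Section 4.2.2 gives the phase 1b estimator: "The DLT rate for a given DL is estimated as total number of DLTs/total number of subjects treated and qualifying for DDS". Table 4-1 labels its decision rows "Decision Based on Total Number of DLTs at the DL". Section 6.7.1 defines DLTs by event: "The occurrence of any of the toxicities outlined in this section will be considered a DLT if occurring within the DLT evaluation period". No section says that a subject with several qualifying toxicities counts once.

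Section 4.2.2.2 sets the closure rule: "A certain DL can no longer be investigated if an additional DLT-free cohort would lead to de-escalation". Its example starts from a state in which "3 out of 4 subjects had DLTs at the next higher DL" and concludes that "regardless of 0, 1, 2, or 3 DLTs, there would be least 3 DLTs for 7 subjects". Closure carries upward: "All DLs with a higher dose than that of the terminated DL should also be terminated".

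Appendix 8 sets the mBOIN target at 30%, with limits of 0.6 and 1.4 times the target, and states thresholds of 24% and 36%. Table 10-5 gives operating characteristics driven by one DLT probability per dose level.

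**The concern.** The BOIN thresholds apply to a proportion: the share of subjects who have at least one DLT, with one yes/no outcome per subject. A count of DLTs divided by subjects is not a proportion. Four DLTs in three subjects would give 133%. When a subject has more than one qualifying toxicity in Cycle 1, the two quantities separate, and Table 4-1 can return a different instruction for the same patients.

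The gap matters most at the first decisions on a level, which come at about 3 or 4 subjects (Section 4.2.2.3), where one extra count can move the call by a full row. The list in Section 6.7.1 has separate entries for haematological and hepatic events, so two distinct DLTs in one subject are possible. At stake is an unneeded de-escalation or a closed dose level, with every higher level closed too.

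**Working it through.** **1. Reproduce the plan's thresholds.** Inputs from Appendix 8: φ = 0.30, φ1 = 0.6 × 0.30 = 0.18, φ2 = 1.4 × 0.30 = 0.42.

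- λ1 = ln[(1−φ1)/(1−φ)] / ln[φ(1−φ1)/(φ1(1−φ))] = ln(0.82/0.70) / ln(0.246/0.126) = 0.2365, stated as 24%.
- λ2 = ln[(1−φ)/(1−φ2)] / ln[φ2(1−φ)/(φ(1−φ2))] = ln(0.70/0.58) / ln(0.294/0.174) = 0.3585, stated as 36%.

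Both match. These formulas assume a binomial count, one outcome per subject.

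**2. Reproduce Table 4-1.** With x the count and n the subjects: escalate if x/n ≤ 0.2365; de-escalate if x/n ≥ 0.3585; terminate if x/(n+3) ≥ 0.3585, which is the closure rule of Section 4.2.2.2. For n = 3 to 9 this gives escalate at up to 0, 0, 1, 1, 1, 1, 2; de-escalate from 2, 2, 2, 3, 3, 3, 4; terminate from 3, 3, 3, 4, 4, 4, 5. All 21 cells match. The table is right when x is the number of subjects with a DLT.

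**3. Read the label literally.** Suppose one subject at the level has DLTs and the others have none.

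| n | Subject count (x = 1) | 2 DLTs | 3 DLTs | 4 DLTs | 5 DLTs |
|---|---|---|---|---|---|
| 3 | Remain | De-escalate | Terminate | no cell | no cell |
| 4 | Remain | De-escalate | Terminate | Terminate | Terminate |
| 5 | Escalate | De-escalate | Terminate | Terminate | Terminate |
| 6 to 8 | Escalate | Remain | De-escalate | Terminate | Terminate |
| 9 | Escalate | Escalate | Remain | De-escalate | Terminate |

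So two DLTs de-escalate and three terminate only at n = 3 to 5. At n = 6 to 8 it takes three and four; at n = 9, four and five.

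**4. Which unit does the rest of the document use?**

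- In the Section 4.2.2.2 example, three subjects with DLTs become three DLTs, and a further cohort of three can add at most three. That holds only with one count per subject.
- The "Terminate a DL" row shows a bare 3 at n = 3 and a ≥ sign in every other column. A bare 3 is complete only if 3 is the maximum.
- The phase 1a rules in Section 4.2.1 speak of subjects who experience DLTs.
- Early stopping in Table 10-5 was compared with a simulation of Table 4-1 (10,000 runs, cohorts of 3, stop at 9 on a level). The event-count rows use assumed shares of DLT subjects with two or three events.

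| % early stopping | Scen. 3 | Scen. 4 | Scen. 5 | Scen. 6 |
|---|---|---|---|---|
| Stated in Table 10-5 | 1.9 | 3.2 | 12.2 | 32.5 |
| Simulated, by subject | 1.7 | 2.9 | 12.5 | 30.5 |
| Simulated, by event, 10% with two | 4.3 | 6.9 | 19.9 | 40.5 |
| Simulated, by event, 20% with two and 5% with three | 10.9 | 15.2 | 33.6 | 54.5 |

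The stated figures fit subject counting. The comparison is limited to early stopping: mean subject totals were not reproduced (scenario 1: 11.3 stated, 15.3 simulated).

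**5. Illustrative size.** Assumption: a share q of subjects with a DLT have more than one; p is the subject-level DLT probability. For 3 subjects:

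P(de-escalate or terminate) = P(at least 2 counts) = 1 − (1−p)³ − 3p(1−q)(1−p)².

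- p = 0.30, subject count (q = 0): 1 − 0.343 − 0.441 = 0.216.
- p = 0.30, q = 0.30: 1 − 0.343 − 3 × 0.21 × 0.49 = 0.348.
- p = 0.30, range of q: 26% at q = 0.10 and 44% at q = 0.50.
- p = 0.20: 0.104 by subject; 0.181 at q = 0.20; 0.219 at q = 0.30.

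P(terminate) at p = 0.30, with exactly two DLTs in 30% of DLT subjects: 0.348 − (3 × 0.09 × 0.49 + 3 × 0.21² × 0.70) = 0.348 − 0.225 = 0.123, against 0.30³ = 0.027 by subject.

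**The case against.** The strongest reply is that the section already settles its own meaning. The worked example, the n = 3 cell, the phase 1a wording and the early-stopping figures all treat a subject as one count, and every boundary stands unchanged. On this view the phrase is loose shorthand that no competent committee would misapply. Table 4-1 is guidance, the Safety Committee endorses each dose level, and the MTD and RP2D are set on the totality of data. Phase 1b also cannot begin without a substantial amendment. All of this stands, and it limits the point to wording. It does not remove it: intent inferred from an example is weaker than an explicit formula and a table heading, and those are what a committee applies.

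A reader might infer that one liver episode meeting the grade 4 ALT, Hy's law and grade 4 irAE entries would count as three DLTs. The documents do not support that. It counts criteria rather than toxicities, and Appendix 3 asks for a diagnosis in place of separate signs. The literal problem needs distinct qualifying toxicities in one subject within 21 days.

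A reader might also take Section 2.3.2.1, which reports more severe cytopenias and severe transaminase increases in phase 1a, as evidence that joint DLTs are common. It does not say that both occurred in the same subjects, and it ties the finding to anti-PD-1/PD-L1 exposure within 6 months, which is now an exclusion.

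**Conclusion.** The point holds as a conflict between the stated estimator and table label on one side and the design's own unit on the other. The boundaries, Table 4-1 and the early-stopping figures are consistent with counting subjects and are not in error.

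It is tempting to conclude that the combination RP2D would be wrong. The documents do not support that: subject counting is the evident intent, the Safety Committee decides, and a literal reading only adds counts. The supportable statement is that the MTD/RP2D could be biased low if the text were followed to the letter, chiefly at 3 to 5 subjects. The rise from 22% to 35% rests on an assumed 30% multi-event share that the documents do not give, so it shows scale and is not a forecast.

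**What to change.** In Section 4.2.2, define the rate as the number of DDS subjects with at least one DLT divided by the number of DDS subjects at that dose level. Relabel the Table 4-1 rows to the number of DDS subjects with at least one DLT, and use the same unit throughout Section 4.2.2.2. No boundary, cohort size or simulation has to change. The cost is a sentence, a table label and a small edit to one example, and all three can go into the substantial amendment that Section 4.2.2 already requires before phase 1b.
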